SPC	Summary of Product Characteristics (in Dutch: officiële productinfomatie IB1-	
	tekst)	
Sponsor	The sponsor is the party that commissions the organisation or performance of	
	the research, for example a pharmaceutical	
	company, academic hospital, scientific organisation or investigator. A party that	
	provides funding for a study but does not commission it is not regarded as the	
	sponsor, but referred to as a subsidising party.	
SUSAR	Suspected Unexpected Serious Adverse Reaction	
Wbp	Personal Data Protection Act (in Dutch: Wet Bescherming Persoonsgevens)	
WMO	Medical Research Involving Human Subjects Act (in Dutch: Wet Medisch-	
	wetenschappelijk Onderzoek met Mensen	
fMRI	Functional Magnetic Resonance Imaging	
PD	Parkinson's disease	

- BOLD Blood Oxygen Level Dependent Activity
- UPDRS Unified Parkinson's Disease Rating Scale
- TRS Tremor Rating Scale

SUMMARY

Rationale: Parkinson's disease is the second most common neurodegenerative disease worldwide. Clinically, Parkinson's disease is characterized by motor slowing (bradykinesia), stiffness (rigidity) and resting tremor. The pathological hallmark of Parkinson's disease is striatal dopamine depletion, but the dopaminergic basis of resting tremor is disputed. For instance, striatal dopamine depletion correlates with all motor symptoms except resting tremor. Furthermore, resting tremor is often resistant to dopaminergic medication. Instead, resting tremor worsens consistently during psychological stress, and recent findings suggest that the noradrenergic (stress) system is hyperactive in Parkinson's disease. Based on empirical (fMRI) data, I have recently proposed a new systems-level model of Parkinson's tremor. According to this model, tremor is initiated in the basal ganglia and amplified in the cerebello-thalamo-cortical circuit. In this study, I will use this model as the basis for understanding how the noradrenergic (stress) system amplifies Parkinson tremor. **Objective**: I will test the hypothesis that the noradrenergic system amplifies tremulous activity in the cerebello-thalamo-cortical circuit. More specifically, I will test how this

Study design: Cross-over intervention study.

modulation takes place (i.e. through which brain regions and connections).

Study population: Two groups of idiopathic Parkinson's disease patients with either a tremor-dominant phenotype (n=40) and with a non-tremor phenotype (n=30). **Intervention (if applicable)**: The intervention only involves the tremor-dominant Parkinson group. To activate the noradrenergic system, I will use a validated and controlled stress-induction task (cognitive-coactivation: alternating blocks of mental arithmetic versus rest). Furthermore, I will test whether a pharmacological intervention (propranolol 40 mg single dose) can counteract the effects of psychological stress on the tremor circuitry. Propranolol is commonly used in clinical practice to treat tremor. The control condition will be a placebo.

Main study parameters/endpoints: (1) Tremor-related activity and connectivity (quantified using concurrent EMG-fMRI); (2) Structural integrity of the locus coeruleus (quantified using neuromelanin sensitive MRI); (3) Clinical tremor severity (quantified using tremor rating scales)

Nature and extent of the burden and risks associated with participation, benefit and group relatedness: The experimental protocol will consist of clinical measurements, and performance of a simple cognitive task in the fMRI scanner. These measurements will be performed on two mornings (duration: 4-5 hours per session). Patients will arrive in a practically defined OFF state, i.e. at least 12 hours after having taken their last dopaminergic medication. At the end of the measurement, they will resume their normal medication regime. When OFF-medication, their Parkinson symptoms may temporarily worsen, which can lead to discomfort. On one session, patients will receive a single dose of propranolol (40 mg). Propranolol is commonly used in clinical practice to treat tremor. This may sometimes lead to temporary side effects such as dizziness, bradycardia, and cold hands/feet. Patients will be extensively monitored during the measurements (blood pressure, heart rate) to avoid any health risks. In addition, our task is designed to induce psychological stress, and this may lead to some discomfort. Finally, the noise in the fMRI scanner, and lying in a small space, may lead to discomfort. If all security measures are fulfilled, then there is not risk for the patients.

Tremor is a common and debilitating symptom of Parkinson's disease. If tremor does not respond to dopaminergic treatment, then there are only few therapeutic options. Better pathophysiological insights are needed to provide a rational basis for improved treatment strategies. This study aims at better understanding the pathophysiology of Parkinson's tremor, by focusing on the noradrenergic system. Identifying the respective neural substrates could potentially have great clinical and therapeutic implications and will also help to better understand why tremor increases dramatically during stressful circumstances. As such, this research may provide clues to target new therapies in tremor-dominant Parkinson patients.

1. INTRODUCTION AND RATIONALE

Parkinson's disease is a very common neurodegenerative disease, clinically characterized by motor slowing (bradykinesia), stiffness (rigidity), and resting tremor. Resting tremor occurs in >75% of patients, and early patients rank it as their second-most bothersome symptom¹. The pathological hallmark of Parkinson's disease is nigro-striatal dopamine depletion², but the dopaminergic basis of resting tremor is disputed³. For instance, striatal dopamine depletion correlates with all motor symptoms except resting tremor⁴, and dopaminergic medication has a variable and sometimes no effect on resting tremor³. On the other hand, resting tremor is consistently amplified during acute psychological stress^{5,6}. Our group has recently shown that the anti-tremor effect of levodopa is reduced in a stressful vs. neutral context⁷ (Fig1). This finding highlights an important clinical problem: patients suffer most from their tremor in stressful circumstances, when available (dopaminergic) therapy is least effective. It also raises interesting mechanistic questions (with potentially broad implications well beyond tremor), namely how stress can affect neural circuitries involved in normal motor function and the generation of pathological disease manifestations. Here, I will investigate the role of the noradrenergic system -which is activated during psychological stress^{8,9}– in the pathophysiology of Parkinson's resting tremor.

[figure not shown]

Fig1: Psychological stress immediately increases tremor (panel A) and reduces the effect of dopamine (panel B⁷).

Several pieces of evidence suggest a link between the noradrenergic system and resting tremor. For instance, post-mortem studies have shown that Parkinson patients with a tremor-dominant phenotype have *less* degeneration of the locus coeruleus (the main source of cerebral noradrenalin) than patients with a non-tremor phenotype¹⁰. Also, nuclear imaging has shown that noradrenalin receptor binding in the locus coeruleus is *increased* in Parkinson

patients vs. controls¹¹, particularly in tremor-dominant patients¹². Furthermore, interventions that suppress noradrenergic hyperactivity, both pharmacologically (beta-blockers¹³⁻¹⁵) and non-pharmacologically (guided relaxation therapy¹⁶) can reduce resting tremor. Conversely, intravenous injection of adrenalin, which activates the cerebral noradrenergic system through the vagal nerve^{8,17}, increases tremor¹⁸⁻²⁰.

Despite these initial findings, the cerebral mechanisms underlying worsened tremor during acute psychological stress remain very much unclear⁵. The locus coeruleus has anatomical projections to all nodes of this circuit²¹. Animal studies have shown that an acute stressor produces motor hyperactivity, possibly mediated through direct effects of noradrenalin onto the cerebral motor circuit²². Another possibility is that noradrenalin interacts with the dopaminergic system. However, acute stress has been associated with increased striatal dopamine release^{23,24}, which would rather lead to tremor suppression than tremor worsening²⁵. It is unlikely that psychological stress influences tremor through the peripheral nervous system, because the effects on tremor emerge almost immediately (Fig1A). Furthermore, adrenalin administration only increases Parkinson's tremor when injected intravenously (i.e. systemically, enabling central effects through the vagus nerve¹⁷), but not when injected into an artery (which distributes adrenalin to the muscle)¹⁹. It is also unlikely that psychological stress modulates tremor through spinal mechanisms^{26,27}. To understand the pathophysiology of Parkinson's tremor, a comprehensive systems-level approach is crucial: different networks are involved, multiple nodes within the cerebellothalamo-cortical circuit have pace-making properties²⁸, and network parameters (interregional connectivity) separate pathological tremor from mimicked tremor²⁹. In my previous work, I have used a systems-level approach to define the cerebral mechanisms underlying Parkinson's resting tremor³. For this purpose, I developed a new method that directly relates cerebral activity (measured with fMRI) to fluctuations in tremor intensity (measured with concurrent EMG; Fig2)^{25,30}. Using this approach, I have shown that tremor is initiated in the basal ganglia, and amplified in the cerebello-thalamo-cortical circuit³. More recently, I have applied network analyses (dynamic causal modelling; DCM) to this tremor circuitry. With DCM, it is possible to test how an extrinsic factor modulates cerebral activity and inter-regional connectivity. The ability to statistically test which underlying network structure best explains the fMRI data sets DCM apart from more traditional fMRI approaches. Using DCM, we have recently shown that dopamine specifically modulates the cerebellothalamo-cortical circuit at the level of the thalamus, but only in a subset of patients with a dopamine-responsive tremor³¹.

We have recently validated an experimental task that reliably modulates Parkinson's tremor (n=33; Fig 2) in a block-wise manner. This task involves alternating blocks of 60 seconds where patients (n=33) either performed mental arithmetic or observed a cross-hair. Importantly, during this task both tremor amplitude (measured with accelerometry) and pupil diameter (measured with eye tracking) rapidly increased during arithmetic blocks and decreased again during rest blocks. This time course allows a block-wise comparison of stress (arithmetic) and control (rest) conditions within one session. We have also behaviourally shown that this stress induction task (which involves cognitive effort) is more successful in modulating Parkinson's tremor (n=17) than a threat of shock task (which involves physical fear).

[figure not shown]

Fig 2: Effect of mental arithmetic (grey; 60 sec) and rest (white; 60 sec) on tremor amplitude (panel A) and pupil diameter (panel B) in 33 Parkinson's disease patients.

[figure not shown]

Fig 3: Method and Hypothesis

2. OBJECTIVES

In the current project, my key objective is to understand the role of the noradrenergic system in the pathophysiology of Parkinson's resting tremor. More specifically, I aim:

1. To define the cerebral mechanisms underlying stress-related amplification of Parkinson's resting tremor, and to test whether these mechanisms are sensitive to a pharmacologic intervention that suppresses noradrenergic hyperactivity (propranolol).

Hypothesis: Based on my previous work, I expect that the noradrenergic system amplifies tremor by acting on the cerebello-thalamo-cortical circuit (Fig2C)²⁵. Given the presence of functional interactions between the noradrenergic and the dopaminergic systems in the basal ganglia^{9,32}, I will also test the alternative hypothesis that the noradrenergic system influences tremor-related activity in the basal ganglia.

2. To test whether the structural integrity of the locus coeruleus-noradrenaline system differs between Parkinson patients with a tremor-dominant and a non-tremor phenotype.

Hypothesis: Based on post-mortem studies, I expect reduced structural integrity of the locus coeruleus in Parkinson patients with a non-tremor phenotype ¹⁰.

 To test whether individual differences in the structural and functional integrity of the locus coeruleus-noradrenaline system can explain individual responses of tremor to stress.

Hypothesis: I expect a positive relationship between the structural integrity of the noradrenergic system and the impact of stress on resting tremor

3. STUDY DESIGN

Interventions

I will manipulate the noradrenergic system using a 2x2 factorial design with factors PHARMACOLOGY (propranolol 40mg vs. placebo) and BEHAVIOR (stress induction vs. control) (Fig3). The two medication conditions (propranolol versus placebo) will be tested on two different days, to avoid carry-over effects. The two behavioural conditions (stress versus control) will be measured on the same day, in a block-wise manner, as shown in Fig 2. The order of the two medication conditions will be counter-balanced. Physiological markers of stress will be monitored throughout the scanning procedure (see below).

Pharmacological suppression of noradrenergic neurotransmission will be achieved using propranolol (40mg, oral dose). This is a non-selective β -adrenergic receptor-blocking agent that competes with β -adrenergic receptor stimulating agents at β 1- and β 2-adrenergic receptor sites. In healthy subjects, propranolol suppresses noradrenergic neurotransmission and functional connectivity within a cerebral salience network⁹. In Parkinson patients, there is mixed evidence regarding the anti-tremor effect of propranolol¹³⁻¹⁵, probably because in most cases contextual factors (stressful vs. neutral) were not taken into account³⁴. Peak plasma concentrations are reached 1 to 2 hours after administration, and remain stable for several hours^{35,36}. Therefore, in line with previous studies⁹, I will administer propranolol (or placebo) 105 min prior to fMRI scanning.

Behavioural noradrenergic stress induction will be achieved using a task that is wellvalidated task by our group, the cognitive co-activation task. This task involves alternating blocks of mental arithmetic versus rest. The dynamics of this task (rapid increases and decreases of both tremor and pupil diameter) make it possible to compare stress and rest conditions within a single fMRI session.

Measurements:

- ECG (on the first visit of the patient, prior to placebo/propranolol).
- Resting state fMRI (10 minutes, concurrent EMG recording). Subjects will be asked to keep their eyes open to continuously monitor their autonomic state. I will use an optimized multiband fMRI sequence with a high spatial resolution (voxel size=2.0 mm isotropic, to extract a reliable BOLD time course from the locus coeruleus) and a high temporal resolution (TR=1000 ms, to optimally correct for physiological noise). Connectivity measures derived from these measurements are used to test Hypotheses #1 and #3 (see *Analyses* below).

- Task-based fMRI (cognitive co-activation; 15 minutes, concurrent EMG recordings). The task will consist of five 60-second blocks during which subjects perform mental arithmetic (which will be displayed on the screen) and five 60-second blocks during which they will focus on a crosshair on the screen. For example, if 200-7 is displayed on the screen, subjects are asked to consecutively subtract 7 from each preceding number. At the end of the task, subjects will indicate how tensed they were (5-point scale).
- Autonomic responses during scanning. To validate our stress induction approach, we will
 record pupil diameter (using eye tracking), heart and respiration rate, blood pressure,
 and salivary cortisol⁹. These outcome measures are used to validate the intervention and
 to test Hypotheses #2 and #3.
- Neuromelanin-sensitive structural MRI scans (10 min) to localize the locus coeruleus and quantify its structural integrity⁴⁰. This scan will only be performed once, since we do not expect an effect of task on structural brain properties. This outcome measure is used to test Hypotheses #2 and #3.
- Rating scales and questionnaires: MDS-UPDRS-III Mini Mental State Examination (MMSE), Tremor Rating Scale, Spielberger's State-Trait Anxiety Inventory, Beck's Depression Inventory, bradykinesia (computer-based peg board test⁴¹) and the Positive and Negative Affect Schedule (PANAS) questionnaire. These measures are used to account for sources of inter-subject variability.
- Color wheel working memory task (45 min, *outside* the scanner). This task measures the preference of individual subjects to perform a stable versus a flexible cognitive effort. This is done by asking participants to perform a visual working memory task on a trial-by-trial basis. There will be two conditions: after remembering a first set of two or four colors, participants are asked after a delay of 2 seconds to either remember a new set of two or four colors (flexibility), OR they are asked to ignore the new set of colors (distraction) and remember the previous set (stability). After this phase of the experiment (15 min + 1- min practice), participants' subjective value of cognitive effort of both conditions will be evaluated. This will be done by presenting participants with a series of choices (15 min). They will have to indicate how much they prefer to redo a block of trials of one condition to the other, or if they prefer not repeating a task at all. In order to ensure validity of the choices, participants will have to redo their selected choice (5 min). The noradrenergic system likely plays an important role in the balance between flexibility (update) and stability (ignore in the face of distraction). We expect that Parkinson patients, in whom the noradrenergic system is dysfunctional, have an

altered balance between flexibility and stability. This task is added to investigate the effect of noradrenergic dysfunction on cognition in Parkinson's disease.

Main Analyses:

Hypothesis 1: I will use EMG-fMRI to test for session-specific differences in the pattern of tremor-related activity (Fig2A)²⁵. I will also use DCM to test how the locus coeruleusnoradrenaline system modulates effective connectivity within the tremor circuit, by contrasting models where behavioral and pharmacological factors modulate different connections and nodes within the tremor circuitry (Fig2C).

Hypothesis 2: I will use correlations between pupil diameter and brain activity³⁹ to test for session-specific differences in the locus coeruleus-noradrenaline system. Pupil diameter is correlated with cerebral activity in the locus coeruleus³⁹, and is regarded as a reliable marker of noradrenergic activity^{42,43}. We have in-house experience with this method (collaboration with [name]). Nuclear imaging (PET) is less suitable for localizing the locus coeruleus-noradrenaline system: well-validated radioligands for the cerebral noradrenaline transporter are lacking, and the limited spatial resolution of PET prevents reliable measurements in the locus coeruleus ^{44,45}. I will also compare the structural integrity of the locus coeruleus, assessed using neuromelanin MR-scanning⁴⁰, between patients and controls.

Hypothesis 3: I will correlate patient-specific tremor-related patterns (#1) with noradrenergic measures (#2), and clinical tremor scores, to predict individual tremor characteristics based on the integrity of the locus coeruleus-noradrenaline system.

[figure not shown]

Fig4: design of the study. Placebo and Propranolol sessions will be counter-balanced.

4. STUDY POPULATION

4.1 Population (base)

Patients with idiopathic PD will be included through their neurologists at the Neurology department of the Radboud University Nijmegen Medical Centre, and through ParkinsonNext (see below). Nijmegen has a very large outpatient movement disorders clinic, and based on previous studies we expect no problems in recruiting enough patients for this research.

Number of subjects:

The full experiment, including testing on two different days, will be performed in 40 idiopathic Parkinson's disease patients with a tremor-dominant phenotype, defined as a resting tremor score of \geq 2 UPDRS points for at least one arm^{3,25}. This number of subjects gives reliable and replicable (validated across multiple cohorts) tremor-related activity^{3,25,31}. Since my focus is to understand how different experimental factors modulate cerebral and clinical correlates of resting tremor, I will use a within-patients (cross-over) design.

In addition, I will perform a subset of measurements in 30 non-tremulous Parkinson patients. These patients will only receive structural MRI scanning, resting state fMRI, and task-based fMRI on one day, to localize structurally and functionally localize the locus coeruleusnoradrenaline system. This group will not receive any intervention (behavioral or pharmacological). I will compare the structural and functional integrity of the locus coeruleus between tremor-dominant and non-tremor Parkinson patients.

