4.4 Sample size calculation

Formal power analyses are impossible given the highly innovative character of our approach. Our projected sample size is based on comparable fMRI experiments in PD. In these studies, a sample size of 20 patients was sufficient to find significant differences non-tremor PD patients and tremor-dominant PD patients ^{25,30}. In addition to tremor-dominant patients, we will also include non-tremor Parkinson patients, matched for age, gender, and non-tremor disease characteristics (duration, severity) with the tremor-dominant group. Here we aim to have two groups of at least 24 subjects (see section 8.5).

On March 19th 2021, data from 17 of 25 (68%) tremor-dominant patients who signed informed consent could be used for further analysis (due to 8 early drop-outs). Data from all 19 included non-tremor patients could be used for further analysis. Furthermore, ongoing data analyses from a previous study, which used the same outcome measure as done here but without a propranolol intervention, showed that 33 of 40 collected data sets contained suitable eye tracking data (83%). Accordingly, we expect that we need to include 40 tremor-

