dominant patients to arrive at ± 24 individuals with complete and high-quality data (40 x $68\% \times 83\% = 23-24$ subjects). Drop-out is much less for the non-tremor group, given that there is no intervention, and only one session. In sum, this means that we will measure at maximum 40 tremor-dominant and 30 non-tremor patients. To avoid more early drop-outs in the tremor-dominant group, we will take the following measures: during screening, we will prioritize patients who have also participated in the Personalized Parkinson's Project (PPP), since a recent ECG is available for these patients. Other patients will be asked whether an ECG has been made recently, if so we will give these patients priority. We will request recent ECGs and only after an MD has approved that it meets all inclusion criteria, patients will be invited to participate. Remaining patients with no ECG available are invited to come to the institute prior to the scheduled sessions, to make an ECG and make sure they can undergo the propranolol intervention. Finally, we will be stricter in selecting suitable patients during our phone screening, and we will not invite patients with a disease duration of >10 years, considerable ON/OFF fluctuations or daily levodopa-equivalent dose of >1200 mg. In addition, shortening the protocol by leaving out the threat-of-shock task will hopefully increase quality of eye-tracking data.

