8.5 Replacement of individual subjects after withdrawal

Our goal is to investigate two groups of 24 patients (tremor-dominant vs. nontremor Parkinson's disease). We count on 6 dropouts per group based on bad eye tracking data, and up to 10 additional dropouts in the tremor-dominant group due to our strict inclusion criteria (ECG and measurement of blood pressure). We will therefore include at maximum 40 tremor-dominant and 30 non-tremor patients.

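### Section 4.1 attaches the full two-day experiment, and the reliability of tremor-related activity, to 40 tremor-dominant patients, but 40 is the inclusion maximum and about 27 to 30 can be expected to give usable data

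*Protocol*

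**What the plan says.** Under the number of subjects, Protocol section 4.1 states: "The full experiment, including testing on two different days, will be performed in 40 idiopathic Parkinson's disease patients with a tremor-dominant phenotype". The next sentence reads: "This number of subjects gives reliable and replicable (validated across multiple cohorts) tremor-related activity". In context, the number meant is 40.

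Section 4.4 declines a formal power analysis and relies on comparable fMRI work, in which "a sample size of 20 patients was sufficient to find significant differences" between tremor-dominant and non-tremor patients. It then reports that by 19 March 2021 "data from 17 of 25 (68%) tremor-dominant patients who signed informed consent could be used for further analysis", because of 8 early drop-outs. It adds an eye-tracking success rate of 33 in 40 (83%) from a previous study, multiplies the two rates, and concludes that 40 must be included to reach about 24 with complete data. It closes with a ceiling: "we will measure at maximum 40 tremor-dominant and 30 non-tremor patients".

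Section 8.5 repeats the target: "Our goal is to investigate two groups of 24 patients (tremor-dominant vs. nontremor Parkinson's disease". It allows 6 losses per group for poor eye tracking and up to 10 more in the tremor-dominant group for ECG and blood-pressure reasons.

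The main endpoint (section 8.1.1) is tremor-related activity and connectivity from concurrent EMG-fMRI. Section 10.1 analyses it in a 2 x 2 repeated-measures ANOVA of stress by propranolol, with four images per subject.

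**The concern.** The same number does two jobs. In section 4.1, 40 is the number who will go through both days, and a claim about reliability hangs on it. In sections 4.4 and 8.5, 40 is the intake from which a smaller analysed group is expected. Both cannot be true under a maximum of 40.

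This matters because the protocol offers little else in support of its size. It gives no power, effect size or standard deviation. The other argument, that 20 patients sufficed, concerns differences between patient groups, not the within-patient drug and stress contrasts of the primary analysis. A reader who relies on section 4.1 would take the main endpoint to rest on 40 two-session data sets of established reliability, and might read a null propranolol result as better supported than it will be.

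**Working it through.** **Inputs.** From section 4.1: 40 patients for the full experiment. From section 4.4: 17 usable of 25 consenting, 33 of 40 with suitable eye tracking, a maximum of 40, and a target of about 24. From section 8.5: a target of 24, with allowances of 6 and up to 10.

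**The plan's own figures.**
- Section 4.4: 40 x 0.68 x 0.83 = 22.6 (with unrounded rates, 40 x 17/25 x 33/40 = 22.4). The protocol prints 23 to 24. The gap is small and is not the point here.
- Section 8.5: 24 + 6 + 10 = 40. This is exact, and it shows that 40 already contains the expected losses.

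**Can 40 complete?** Section 4.4 applies its consent-based rate to the 40, so the 25 patients who had consented count towards the maximum. That leaves 40 - 25 = 15 places. If none of those 15 is lost, the usable number is 17 + 15 = 32. For 40 usable data sets at 68%, 40 / 0.68 = 58.8, so about 59 patients would have to consent.

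**Expected number before eye-tracking loss.**

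| Basis | Calculation | Usable |
|---|---|---|
| Section 4.4 rate | 40 x 0.68 | 27.2, about 27 |
| Section 8.5 allowance | 40 - 10 | 30 |
| Upper bound | 17 + 15 | 32 |

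Reaching 30 would need 30 - 17 = 13 of the remaining 15 to succeed (87%), which depends on the new screening measures working.

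**Uncertainty of the rate.** The exact 95% interval for 17/25 is 46% to 85%. Applied only to the 15 places still open, it gives 17 + 15 x 0.465 = 24.0 to 17 + 15 x 0.851 = 29.8.

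**Which number belongs to the main endpoint.** The last step down to 24 is eye-tracking loss. The main endpoint uses EMG and fMRI, and nothing in sections 8.1.1 or 10.1 requires usable pupil data. So 27 to 30 is the relevant range for the main endpoint, and 24 is the target for complete data including eye tracking.

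**Illustration only.** The protocol states no test level or power. Assume a single paired t-test, two-sided 5%, 80% power, with the effect in units of the SD of the within-patient difference:

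| n | Detectable effect (SD) |
|---|---|
| 40 | 0.45 |
| 32 | 0.51 |
| 30 | 0.53 |
| 27 | 0.56 |

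Under these assumptions, the detectable effect at 27 to 30 is 16% to 23% larger than at 40 (0.529 / 0.454 = 1.17 and 0.560 / 0.454 = 1.23 from the unrounded values).

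**The case against.** The strongest reply is that nothing is hidden. Section 4.4 prints both rates, the target and the ceiling, and section 8.5 itemises the losses. Anyone who reads the sample-size section will not expect 40 analysed data sets. On this view the defect is one sentence in section 4.1 that was not brought into line. That is a fair account of its extent, but disclosure elsewhere does not correct section 4.1. It is what creates the contradiction.

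Several other replies stand and limit the point:

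- A reader might infer that reliability is lost below 40. Section 4.1 does not say that fewer would be unreliable, section 4.4 reports that 20 sufficed in comparable work, and 27 to 30 exceeds 20. The sizes of the cohorts cited in section 4.1 are not given. Equally, the figure of 20 does not establish adequacy for the stress-by-propranolol contrasts.
- A reader might see a conflict in citing reference 25 both for 40 and for 20. The two citations support different statements, and 20 being sufficient is compatible with 40 being reliable.
- The Summary gives n=40 only as a description of the study population. It makes no claim about completion or reliability, so it is not in error.
- A reader might say that the protocol overstates its power or precision. It states neither, so the detectable effects above are an outside benchmark. They also use one paired test, whereas the plan has a 2 x 2 ANOVA over regions of interest, and the stress-versus-rest contrast can be estimated within a single session.
- The 68% was observed before ECG review ahead of invitation and stricter telephone screening were introduced, so 27 is a projection.

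**Conclusion.** The point holds as a contradiction about the stated size. Section 4.1 says 40 will undergo the full experiment and rests a reliability claim on that number. Under the protocol's own maximum and the losses already recorded, no more than 32 can give usable data, and about 27 to 30 is the reasonable expectation before eye-tracking loss. That is 25% to 33% below 40 (10/40 = 25%; 12.8/40 = 32%, or 13/40 = 33% after rounding to 27).

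This rests on three assumptions: that the 25 consenting patients count towards the 40, that data usable for further analysis means usable data from both sessions, and that poor eye tracking does not exclude a patient from the EMG-fMRI analysis. The first follows from how section 4.4 does its arithmetic. The other two are close readings that the protocol could confirm.

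The conclusion stops there. The documents do not show that the design is unreliable or underpowered at 27 to 30, only that the argument for its size is attached to a number that will not be analysed.

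**What to change.** In section 4.1, replace the statement that 40 will undergo the full experiment with three numbers that agree with sections 4.4 and 8.5: up to 40 tremor-dominant patients included; about 27 to 30 expected to give usable two-session data for the EMG-fMRI main endpoint; and 24 as the target with complete data including eye tracking.

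Attach the reliability sentence to the number expected to be analysed and give the sample sizes of the cited studies, or delete it. It would also help to say whether a patient with poor eye tracking stays in the main analysis.

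A detectable effect could be added if the sponsor wishes, with its assumptions stated, but it is not needed to remove the contradiction.

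The cost is wording only. No extra patients are needed and no analysis changes. The stated size becomes less favourable.
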